#### **Passive range of motion or passive stretching:**

Participants assigned to the passive exercise and Vitamin D group will have their caregivers perform passive ROM. Caregivers will be instructed to sit on a stool, cup the participant's leg above the ankle joint, and move it from 90-degrees of knee flexion to full knee extension. The leg will be maintained in extension for 5 sec and returned to flexion for 5 sec. The passive actions are repeated in the manner described in the RT protocol; 10 reps on the right leg followed by 10 reps on the left leg for 4 sets x 10 reps. This exercise training will take place twice a week. Each training exercise will last 30 – 40 minutes each day of the exercise.

**Blood Pressure (BP) Monitoring:** The caregiver will measure the participant's BP before starting the exercise, record the reading and leave the BP cuff in place. About 15 to 20 minutes into the exercise, another BP reading will be taken and the final reading at the end of the exercise to safeguard against Autonomic Dysreflexia (AD). Most individuals with high cervical and thoracic levels of SCI own BP machines. However, if they do not own one, they are eligible to get one from their Providers.

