**Resistance training (RT):** Participants and caregivers will be trained on RT (application of electrodes, initiating and adjusting currents and the application of ankle weights). Resistant Training will be performed twice weekly **in an open-chain format (resistance is placed at the distal part of an extremity in a fixed position) in the first 4.5 mos, followed by 4.5 mos in a closed-chain format using surface NMES.** Initial open-chain format ensures muscle hypertrophy that is likely to cause modest bone adaptations, prior to it being subjected to significant loading during closed-chain format. This would ensure bone safety during the close kinematic exercise. No ankle weights in the first week to ensure full knee extension against gravity. Weekly increments of 2 lbs. will be used on the condition that full knee extension is achieved before any increase in load. NMES of the extensor muscles of the knee, for concentric-eccentric actions will be by surface electrodes as shown in **fig 1**. Two 8 X10 cm^2 (Uni-Patch, Wabasha, MI, USA) adhesive carbon electrodes will be placed on the skin over the knee extensor muscle group. Current from the stimulator will be increased at 5-second intervals to evoke full knee extension against gravity followed by the lengthening action during relaxation. The current (mA) that causes full knee extension will be recorded. Training will be performed remotely, twice weekly for 4 sets of 10 repetitions under full supervision from the PI **by telehealth**. Each RT session will consist of 4 sets of 10 repetitions of NMES-induced knee extensions for 60 min. A 5 sec/5 sec work/rest ratio will be used with 3 min rests between sets, 30 Hz, 1 ms pulses and current

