to the VVC by placing electrodes, ensuring the batteries of the stimulator are charged overnight, connecting the electrodes to the stimulator and positioning the ankle weights. Once the setup is completed and internet connection established, the participant is instructed to increase the current to bring the leg into full knee extension and then report the current in milliamps (mA) to the PI. The goal is for each participant to perform 4 sets of ten repetitions. Each exercise training session will be conducted for at least 30 min with 2-3 min of rest periods between each set and 5 sec between each repetition. At the end of each session, the PI confirms the next appointment, reminds participant to confirm next appointment online 24 hours before, and access their log in password. Our telehealth platform is well established with strong support from our IT department. It is unlikely to fail but should it fail, participant will be rescheduled for the next day.

**Measurements: Specific aim 1. MRI:** MRI with no contrast will be performed using a 3 Tesla magnet (GE). The skeletal muscle CSAs will be determined at baseline and 9 months, respectively. Both lower limbs will be strapped together using soft Thera-band to avoid any movement inside the magnet. Participants will be instructed to lie still inside the magnet and they will be provided with earplugs to protect their ears against the magnet noise. Duration of the whole scan including preparation time should not exceed 10 min. Images of both thighs will be obtained with the following scanning parameters (repetition time, 500; echo time, 14; field of view, 20cm; matrix, 256×256). Transaxial images, 8 mm thick and 4 mm apart, will be taken from the hip joint to the knee joint using a localized coil. A specific knee coil will be used to capture trabecular bone parameters of the distal femur and proximal tibia. Images will be downloaded and analyzed using X-vessel software for muscle/cortical bone CSAs, as previously conducted by our group.

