Falls could occur during transfers with sliding board or portable lift from bed to wheelchair and from wheelchair unto intervention equipment (rowing machine). This requires careful use of equipment. To avoid this kind of accident, transfer techniques will be reviewed with participants and caregivers (where applicable) at the beginning of the study. However, this rarely occurs after a Veteran has successfully completed rehabilitation treatment post injury.

- Protection against risk of fracture

Every effort will be taken to minimize possible bone fracture; DXA scan will be performed as detailed earlier prior to enrollment in the trial. Persons with T-score less than -2.5 SD at the hip joints or with bone mineral density less than 0.6 gm/cm^2 at the knee joints will be excluded from the trial.

- Protection from autonomic dysreflexia

Blood pressure (BP) will be monitored closely during the entire intervention and established AD protocol followed should participant experience AD symptoms (patients and caregivers usually receive training on AD management at home, during their rehabilitation course). Any significant rise in BP greater than 20 mmHg above resting BP, the intervention will be suspended immediately and AD protocol instituted. The PI will remain on video connection until AD symptoms resolved and participant returns to normal state.

- **Protection against medications adverse effects**

Medication associated with the current trial can cause allergic reactions, such as, rashes, nausea, vomiting, and hypercalcemia. The PI will obtain allergy history (prior reactions) and monitor the patient and blood parameters closely during the course of the trial to avert any serious drug reaction.

**Study removal criteria may include:** Participants may be withdrawn from the study by the research team for the following concerns:

1. New medical diagnosis of carcinoma of the breast or prostate as these would may have bone health implications. Deep venous thromboembolism as this will hinder intervention and may increase risk of pulmonary embolism; stroke, hypertension, serious heart problems, heart failure, myocardial infarction, ventricular arrhythmia, exertional chest pain, insulin dependent diabetes, hypercholesterolemia, hypertriglyceridemia, impaired liver function, hypercalcemia, or significant renal dysfunction.
2. Hospitalization for acute medical problems (e.g. Liver enzymes (AST / ALT) >1.5 times normal upper limit).

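### The rule that stops exercise at a BP rise above 20 mmHg has only one scheduled reading per session on which it can act; readings at the end of each set would close most of the gap cheaply

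*Combined protocol and SAP*

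**What the plan says.** Under Protection Against Risk, the item on autonomic dysreflexia says BP "will be monitored closely during the entire intervention" and sets a numeric stopping rule: "Any significant rise in BP greater than 20 mmHg above resting BP, the intervention will be suspended immediately and AD protocol instituted". AD symptoms start the AD protocol as well, and "The PI will remain on video connection until AD symptoms resolved and participant returns to normal state".

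The reading times appear in one place, the Blood Pressure (BP) Monitoring paragraph that follows the description of passive range of motion. The caregiver measures BP before exercise and is to "record the reading and leave the BP cuff in place". Then: "About 15 to 20 minutes into the exercise, another BP reading will be taken and the final reading at the end of the exercise". The paragraph gives AD as the reason for these readings. I take it to apply to both arms.

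The Resistance training (RT) paragraph describes remote training "twice weekly for 4 sets of 10 repetitions under full supervision from the PI" by telehealth, and adds: "A 5 sec/5 sec work/rest ratio will be used with 3 min rests between sets". The longer Home Video Telehealth Service paragraph gives "2-3 min of rest periods between each set". The control arm's passive movements follow the RT pattern. The two rowing descriptions state no rest between sets.

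**The concern.** A numeric threshold works only when a number is taken. The rule is meant to act at once on a rise above 20 mmHg, and it stands apart from the symptom trigger, so the authors intended BP itself to stop a session. Yet the schedule gives it one opportunity per session. A noticed symptom would be acted on in any case. A rise without symptoms cannot be seen on video; only a cuff reading shows it.

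What is at stake is participant safety, not an endpoint or an estimate. Eligible injury levels run from C8 to T10. The Risk to Subjects table singles out cervical levels and T6 and above for dysreflexia, so part of the eligible range is the part most prone to it, and training takes place at home.

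**Working it through.** **Count of readings.** Scheduled: 3 (before, about 15-20 min, end). The first is the resting reference. At the last there is no exercise left to suspend, although it can still start the AD protocol. Readings that can stop a session: 3 − 2 = 1.

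**Inputs for the timeline.**
- Four sets of 10, hence three between-set rests, of r = 2 to 3 min.
- Session length T is 30-40 min in the intervention descriptions and about 60 min in the Resistance training (RT) paragraph and under Subject's burden. The 60 may include set-up, so I show each basis separately.
- Rep timing is 5 s work and 5 s rest, 10 s per rep. With 10 reps on each leg, a set takes 20 × 10 s = 200 s = 3.33 min.

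**Longest interval now.** With the mid-session reading at time m, it is max(m, T − m).
- T = 30: m = 15 gives 15; m = 20 gives 20.
- T = 40: m = 15 gives 25; m = 20 gives 20.
- T = 60: m = 15 gives 45; m = 20 gives 40.
- Stated rep timing, rests between sets only: T = 4 × 3.33 + 3r = 19.3 to 22.3 min. The longest interval is the 15-20 min before the reading, or the whole session if it ends first. With 3 min rests the third set runs from about 12.7 to 16 min, so the single reading comes late in the third of four sets or afterwards.
- Stated rep timing, a rest after each leg: T = 8 × 1.67 + 7r = 27.3 to 34.3 min. The longest interval is again 15-20 min.

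**Longest interval with a reading at the start of each between-set rest.** With equal sets filling T, a set lasts s = (T − 3r)/4 and the interval is s + r.
- T = 30: 6.0 + 2 = 8.0; 5.25 + 3 = 8.25.
- T = 40: 8.5 + 2 = 10.5; 7.75 + 3 = 10.75.
- T = 60: 13.5 + 2 = 15.5; 12.75 + 3 = 15.75.
- Stated rep timing: 3.33 + r = 5.3 to 6.3. With a rest after each leg: 3.33 + 2r = 7.3 to 9.3.

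| Basis | Now (min) | With end-of-set readings (min) |
|---|---|---|
| 30-40 min session | 15-25 | about 8-11 |
| 60 min session | 40-45 | about 16 |
| Stated rep timing (19-22 or 27-34 min) | 15-20 | about 5-9 |

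These figures give no credit for keeping the reading taken during exercise, which can only shorten the intervals.

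**Extra suspensions.** Readings that can stop a session rise from 1 to 4, or to 3 if the mid-session reading coincides with a rest. The documents give no trigger rate, so q, the chance that one reading exceeds the threshold, is an assumption, as is independence between readings. Over 39 weeks × 2 = 78 sessions, expected stops per participant are 78 × [1 − (1 − q)^k] for k readings.
- q = 0.5%: 0.4 (k = 1), 1.2 (k = 3), 1.5 (k = 4).
- q = 5%: 3.9 (k = 1), 11.1 (k = 3), 14.5 (k = 4).

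**The case against.** The strongest reply is that the two sections fit together. The three readings can be read as a minimum, with others taken as needed to meet the promise of monitoring throughout. The cuff stays on for that purpose, the PI watches live, and symptoms trigger the AD protocol without any reading. The AD protocol and the standard operating procedures that the plan relies on are not reproduced, and may set a closer interval. How often to read a cuff in a supervised session is a clinical judgement.

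Much of this stands. A reader might infer that participants exercise unmonitored between readings, or that the plan makes no provision for a rise in that time. The documents do not support either: supervision is continuous and unscheduled readings are possible. What remains is narrower. Nothing in the written schedule prompts an extra reading when there are no symptoms, and that is the case the numeric rule adds to the symptom trigger.

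Two further objections shape the remedy. First, the Risk to Subjects table names the weights and the exercise as the possible noxious stimulus, so reading only during rests could miss the peak. The reading during exercise should therefore stay, and the new ones should be taken as each set ends. Second, more readings mean more stops, and arm-assisted rowing could concentrate them in the experimental arm. Both are fair.

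A reader might also infer that rowing sessions have no rests at all. That is not established: the telehealth paragraph speaks of training sessions in general, though its set-up text mentions ankle weights, so whether it covers rowing is unclear.

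**Conclusion.** The point holds as a low-cost safety improvement. One scheduled reading per session can trigger the suspension rule. On a like-for-like basis, end-of-set readings cut the longest interval without a scheduled reading to roughly half or less. This assumes that the published schedule is the operative one, that sets are of equal length, and that readings are taken at the start of each rest.

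The residual risk is small and cannot be quantified. The PI is on live video, the Human Subject Section excludes uncontrolled autonomic dysreflexia, and the Risk to Subjects table rates the event as rare. The documents give no frequency for symptom-free rises. A reader might infer that the trial is unsafe or that its results are compromised; nothing here supports that.

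**What to change.** Amend the Blood Pressure (BP) Monitoring paragraph as follows:
- Add a reading as each set ends, at the start of each existing 2-3 min rest. Keep the pre-exercise reading, the one during exercise and the final one.
- For rowing, require the same end-of-set reading or a fixed maximum interval, so that the rule does not depend on whether rests apply.
- Have the caregiver report each reading to the PI on video.
- Have the study's SCI physicians confirm the schedule and state whether the 20 mmHg is systolic and whether a repeat reading must confirm it before suspension.

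The cost is a short amendment, matching caregiver instructions and about three more cuff readings per session. The cuff is already on and the caregiver already takes the readings, so no session time is added if a reading fits within the rest. The real downside is more suspensions under the plan's own rule, with up to three to four times as many chances to trigger it. That could slightly reduce the training dose, possibly more in the experimental arm. A confirmatory reading would limit stops that are not due to dysreflexia.

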#### **Home Video Telehealth Service:**

Telehealth is a service offered by the VA for use to provide virtual care. Telehealth uses video conference calls. Suppose participants are not already enrolled in the VA Telehealth program. In that case, they will be given a registration form to complete to provide us permission to use VA Telehealth before they can participate. The participants will need to have a smartphone, a tablet, or a computer with a webcam and

internet access to be able to participate. However, if they not have one of these, they will be provided a tablet with a web camera and internet access, and we will help them create an e-mail account if they do not already have one.

The participants will need a quiet space in their homes for the training. The study team will make sure that the address is accessible to EMS in an emergency. If it is not accessible to EMS, they may not participate in the study. At the start of each session, the PI will verify the address and telephone number and an alternate contact person, and a phone number for use in emergencies or communication failure. Should the need arise, the study team will contact EMS or the National VA Telehealth Crisis Line for additional help.

Before starting the exercise training session, the microphone, speakers, and web camera will be tested to ensure things are working fine from both ends. We will request participants to be ready 20-30 min before the video call by asking the caregivers to place the electrodes on their legs, make sure the batteries of the stimulator are fully charged, electrodes are connected to the stimulator, and the ankle weights are positioned. Once the setup is completed, and the Telehealth connection is established, the training will begin.

All training sessions will be conducted twice weekly. At the end of each session, the PI will confirm the next appointment and request that the participant confirms his/her next appointment online 24 hours before the next session. If unable to keep the next appointment for any reason, we can reschedule the appointment for another day and time so long as participants can have two sessions in a week.

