**Dual energy x-ray absorptiometry (iDXA):** iDXA will be used to measure bone composition including regional and total *Fat Mass (FM)*, *Fat Free Mass (FFM)*, cortical porosity, and BMD. Total body and regional scans will be performed using an iDXA scanner (Lunar Inc., Madison, WI) bone densitometer to determine regional BMD and total body T-score, Total hip BMD and knee BMD scores (Total body T-score less than -2.5. Total hip BMD T-scores < -3.5 and knee BMD scores of less than 0.6 g/cm^2, will be excluded). Testing is performed after lower extremity elevation for at least 20 min to minimize fluid shift. Scanning and analysis is certified by DXA operator. The participant is assisted to lie on a padded table with both legs strapped proximal to the knees and ankles. The arms and legs are properly aligned to allow participant to lie still for 10 min during the scan. Total and regional FM and FFM are determined with DXA software in order to control for confounding variables; fat mass and BMF may influence bone health. The coefficient of variability of two repeated scans is < 3%.

**Specific aim 2:** We will assess bone remodeling with the following bone biomarkers: *BALP*, *P1NP* and *CTX*, 25(OH)D, PTH, renal panel, magnesium and calcium levels at baseline, 4.5 mos and 9 mos. HgbA1c will be obtained prior to and post intervention to determine glucose uptake benefit resulting from the intervention. Blood samples not exceeding 10 mls will be obtained after 8-10 hours overnight fasting. Samples will be processed at CVHCS Clinical Pathology Laboratory or Quest diagnostic depending on negotiated cost. All tests will be performed at the VAMC and participants transportation to and from test will be sponsored.

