3. Serum calcium greater than 16mg/dL or symptoms of hypercalcemia
4. Severe peripheral edema, classified as 2+ or higher
5. Any SAE that the SCI physician, [name], deems necessary for withdrawal for participant's safety.

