### **Subject's burden:**

The current study **was designed to reduce and minimize participants' burden** including transportation and participation time. Although participation may impose a significant burden, every effort will be taken by the study team to reduce the stressors and burden associated with study participation over the study period. Each intervention session would last approximately 60 minutes. The current study is designed to allow participants to participate from the comfort of their homes using video telehealth technologies. This should provide some level of control over most SCI factors that may otherwise impact the outcome of the study, for example, stress associated with travel burden that could lead to attrition. Each participant will have the liberty to miss up to

15% of scheduled Telehealth visit, due to unanticipated events, such as, short duration of acute illness, medical appointments, or vacation, without being asked to withdraw or disenrolled from the study. We believe that we can retain participants through the duration of the study (9 months) by:

- a) Providing free transportation for tests at the medical center (most Veterans already have this benefit).
- b) Providing flexible hours to accommodate education and work-related schedules.
- c) During data collection, we will provide sufficient time for participants to have their meals and use medications.
- d) Using a comprehensive team approach that would allow participants to engage in recreational activities and avail themselves of Psychology (if desired) and Nutritional services.

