### **Data and Safety Monitoring Plan.**

The PI will monitor and review the protocol as well as data collection every month to evaluate participants' safety, data quality, and study progression and execution. The PI will review the protocol for any major concerns prior to implementation. The local data monitoring board will meet every 6 months to review/discuss the study. The data monitoring board will have the option to request stopping or cessation of participants' enrollment and all research procedure, if deemed necessary. It is unlikely that they would find significant improvement in collected bone parameters at mid-intervention (4.5 months) in the intervention group because bone requires a longer time for adaptation, especially in persons with SCI. However, should there be significant improvement (s) in the intervention group compared to the control group, the data monitoring team could terminate the study early. The PI will also assess the performance of overall study operations and any other relevant issues, as necessary. The Data and Safety Monitoring Board (DSMB) is responsible for overseeing the safety of the research and report observations/findings to the IRB on an annual basis. The data monitoring team will review all unanticipated problems involving risks to subjects or others associated with the protocol and provide an independent report of the event to the IRB. They may discuss the research protocol with the investigators; shall have authority to stop a research protocol in progress, remove individual human subjects from a research protocol, and take whatever steps necessary to protect the safety and well-being of human participants until the IRB can assess the monitor's report; and shall have the responsibility to promptly report their observations and findings to the IRB. A letter will be drafted from the DSMB and will be attached with the annual summary report to the IRB. Elements in the letter will include the followings:

- Evidence of study-related AEs

- Evidence of efficacy according to pre-established statistical guidelines, if appropriate;
- Data quality, completeness, and timeliness
- Performance of the specific research center
- Adequacy of compliance with goals for recruitment and retention
- Adherence to the protocol
- Factors that might affect the study outcome or compromise the confidentiality of the trial data (such as protocol violations)

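### Participants may be withdrawn from the study, and the plan does not ask those who stop training to complete the remaining outcome tests

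*Combined protocol and SAP*

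**What the plan says.** All references are to the combined protocol and SAP.

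- **Study removal criteria** (under Protection Against Risk): "Participants may be withdrawn from the study by the research team for the following concerns". Item 1 names 15 conditions if breast and prostate carcinoma count as one, ending with "insulin dependent diabetes, hypercholesterolemia, hypertriglyceridemia, impaired liver function, hypercalcemia, or significant renal dysfunction". Items 2 to 5 add hospitalization, "Serum calcium greater than 16mg/dL or symptoms of hypercalcemia", severe edema, and serious adverse events that the SCI physician judges to require withdrawal.
- **Data and Safety Monitoring Plan:** the monitoring team may "remove individual human subjects from a research protocol".
- **Subject's burden:** participants may miss up to 15% of scheduled telehealth visits "without being asked to withdraw or disenrolled from the study". What happens above 15% is not stated.
- **Home Video Telehealth Service:** missed sessions can be made up. One description says "we can reschedule the appointment for another day and time so long as participants can have two sessions in a week". The other, on a technical failure, says "should it fail, participant will be rescheduled for the next day".
- **Measurements:** MRI and DXA are at baseline and 9 months. The Aim 2 bloods are at baseline, 4.5 and 9 months, including "renal panel, magnesium and calcium levels at baseline, 4.5 mos and 9 mos".
- **Data Analysis Plan:** a baseline-adjusted ANCOVA compares the groups after the intervention. No analysis set or missing-data rule is given.
- **Detailed Strategies for the Recruitment Plan:** no attrition is expected.
- **Sample Size Justification:** 10 per group. One purpose is to estimate an effect size for a larger randomised trial.

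**The concern.** The removal wording acts on study membership, not on training alone. The only stop that applies to training alone is the suspension of a session when blood pressure rises, and that is a within-session safety rule. A participant who is withdrawn, or who leaves over attendance, therefore has no stated route to the remaining outcome tests.

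The reasons for leaving arise after randomisation and concern health or adherence, which may be related to the outcomes. Hypercalcemia and renal dysfunction, for example, are removal reasons and also relate to blood measures scheduled in Aim 2. If such people have no 9-month value, the ANCOVA compares those who stayed well and attended, not those who were randomised. With 10 per arm, each person lost is 10% of an arm. The main thing at stake is the effect size carried into the next trial.

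**Working it through.** **1. Is there any instruction to test people who have stopped?** The places where one might expect it:

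| Section | What it provides | Does it ask for the remaining tests after stopping? |
|---|---|---|
| Measurements | General test schedule for all participants | No mention of withdrawn participants |
| Process for obtaining informed consent | Voluntary withdrawal at any time | No |
| Protection Against Risk | Extra visits after an adverse event | For safety only |
| Adverse Events | Review of dropout and withdrawal reasons every ten days | Reasons only, no outcome data |
| Data and Safety Monitoring Plan | Board letter covers data completeness and retention | Monitoring only |
| Data Analysis Plan | ANCOVA on post-intervention values | No rule for missing values |

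None does. This covers the protocol body; the consent form was not available to check.

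**2. The plan's own figure.** Inputs from Sample Size Justification: n = 10 per group, d = 0.9, alpha = 0.25. Sidedness is not stated. For an unadjusted two-sample t-test, the noncentrality is d / sqrt(1/n1 + 1/n2) = 0.9 / sqrt(0.2) = 2.01 on 18 degrees of freedom. Two-sided power is 79.6%, which matches the stated 80%. One-sided power would be 90.7%, so two-sided is inferred.

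**3. Precision if testing ends at withdrawal.** The numbers lost are assumptions. The approximate 95% half-width for d is 1.96 × sqrt(1/n1 + 1/n2 + d²/(2(n1+n2))), with d = 0.9. At 10 v 10 this is 1.96 × sqrt(0.2 + 0.02025) = 0.920.

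The ANCOVA column assumes a baseline-to-9-month correlation of 0.5, which the documents do not give. It replaces d by 0.9 / sqrt(1 − 0.5²) = 1.039 and uses n1 + n2 − 3 degrees of freedom.

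| Analysed | Power, unadjusted t | Power, ANCOVA (assumed r = 0.5) | Half-width for d, unadjusted |
|---|---|---|---|
| 10 v 10 | 79.6% | 87.0% | 0.920 |
| 8 v 10 | 76.2% | 84.0% | 0.975 |
| 8 v 8 | 73.0% | 81.0% | 1.028 |

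Losing 4 of 20 widens the interval by 1.028 / 0.920 − 1 = 12%.

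**4. Selection.** If k of 10 in an arm are lost, the mean of those kept differs from the full-arm mean by (k/10) × (mean kept − mean lost). Both inputs are assumptions.

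- k = 1, difference 0.5 SD: 0.05 SD, or 0.05 / 0.9 = 6% of the planning effect.
- k = 2, difference 1 SD: 0.20 SD, or 0.20 / 0.9 = 22%.

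One concrete case: d is 0.9 among those kept, and 2 of 10 in the stimulation arm are lost who would have had no benefit. The as-randomised d is (8 × 0.9 + 2 × 0) / 10 = 0.72. Required sample size varies as 1/d², so a later trial sized on 0.9 would have (0.72 / 0.9)² = 64% of the participants needed. If both arms lost similar people in similar numbers, the shifts would largely cancel in the comparison.

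**The case against.** Much of the opposing case stands.

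- **Removal is not automatic.** A reader might infer that the listed events force participants out. The text is permissive, and entry screening already excludes several of the conditions, so removals may be few. Stands.
- **15% is not a stated disenrolment rule.** It is an allowance, and the consequence of exceeding it is only implied. Rescheduling may mean the limit is rarely reached. Stands.
- **Differential loss by arm is not shown.** It is tempting to argue that stimulation, weights and rowing will drive more withdrawals in one arm. The documents tie no listed removal reason to those elements. Vitamin D, the element they link to hypercalcemia, goes to both arms. Stands: this is conjecture.
- **The stated power is not shown to be wrong.** It reproduces, and the unadjusted figures do not describe the planned ANCOVA, which could keep about 80% power at 8 v 8 if the correlation were 0.5. Stands: power is not the reason to act.
- **This is a pilot.** Testing efficacy is not its primary goal, its primary analyses are mainly descriptive, and a 0.20 SD shift is small beside a half-width of 0.92. This lowers the stakes. It does not remove them, because the effect estimate is a stated product of the pilot.
- **The consent form might cover follow-up after withdrawal.** Possible. The protocol should still say so, since the ANCOVA depends on it.

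None of this supplies the missing instruction to keep testing people who stop training.

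**Conclusion.** The concern holds in a limited form. The plan allows, and does not require, withdrawal from the study for post-randomisation events, and implies the same for poor attendance. It does not separate stopping training from leaving the study or ask for the remaining tests. Followed as written, it could leave the 9-month comparison and the effect size for the next trial resting on participants selected by health or adherence.

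The size and direction of any bias are unknown, because the documents give no withdrawal rate. The shift of 0.05 to 0.20 SD rests wholly on assumed losses of 1 or 2 in one arm and an assumed difference of 0.5 to 1 SD. The loss of precision is modest. This should be changed because the remedy is cheap and a 9-month scan that was not taken cannot be recovered. No clinical criterion is questioned, and no figure in the plan is shown to be wrong.

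**What to change.** 1. **Study removal criteria and Subject's burden:** distinguish stopping training from leaving the study, and leave the clinical criteria unchanged. Ask anyone who stops training, with consent and if safe, to have the remaining planned tests: Aim 2 bloods at 4.5 and 9 months, MRI and DXA at 9 months. State that missed sessions alone do not end outcome testing.
2. **Data Analysis Plan:** analyse participants in their assigned arm whatever their attendance. Report by arm the number of missing 9-month values and the reasons for stopping. The reasons are already reviewed under Adverse Events, so only the reporting by arm is new.

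**Cost:** a few sentences, plus follow-up tests in the few people who stop training. These tests are already planned for all 20, and Specific aim 2 says transport is sponsored. Limitations and Alternatives, item 6, allows local testing for participants at Spokes sites, but Measurements places all measurements at the main laboratory, so the saving from local testing is uncertain. The estimated effect may be smaller, because people who stopped training stay in the comparison.
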